### **CNGA3CNGA3 Gene Therapy trial for Achromatopsia**

---

The Case Report Forms (eCRFs) will not bear the participant's name or other personal identifiable data. The participant's date of birth and trial identification/participant number will be used for identification.

For other information regarding Data Management please see Section 5.10.2.

## **6.7 Declaration of Interests**

The trial is funded by MeiraGTx UK II Ltd.

██████████ declares ownership of minority shareholdings in MeiraGTx UK II Ltd. and receipt of payment from MeiraGTx UK II Ltd. for consultancy services.

██████████ declares ownership of minority shareholdings in MeiraGTx UK II Ltd. and receipt of payment from MeiraGTx UK II Ltd. for consultancy services.

## **6.8 Indemnity**

MeiraGTx UK II Ltd. holds insurance to cover participants for injury caused by their participation in the clinical trial. Participants may be able to claim compensation if they can prove that MeiraGTx UK II Ltd. has been negligent. However, as this clinical trial is being carried out in a hospital, the hospital continues to have a duty of care to the participant in the clinical trial. MeiraGTx UK II Ltd. does not accept liability for any breach in the hospital's duty of care, or any negligence on the part of hospital employees. This does not affect the participant's right to seek compensation via the non-negligence route.

Participants may also be able to claim compensation for injury caused by participation in this clinical trial without the need to prove negligence on the part of MeiraGTx UK II Ltd. or another party. Participants who sustain injury and wish to make a claim for compensation should do so in writing in the first instance to the Chief Investigator, who will pass the claim to MeiraGTx UK II Ltd's. insurers.

Hospitals selected to participate in this clinical trial shall provide clinical negligence insurance cover for harm caused by their employees and a copy of the relevant insurance policy or summary shall be provided to MeiraGTx UK II Ltd. upon request.

## **6.9 Finance**

The trial is fully funded by MeiraGTx UK II Ltd. It is not expected that any further external funding will be sought.

## **6.10 Archiving**

### **6.10.1 Archiving of Essential Trial Documentation**

Requirements for a traceability system and document archiving will be met in line with Regulation 1394/2007 on Advanced Medicinal Products and the applicable Directives therein. To comply with the regulatory requirements, each responsible party (the sponsor of the trial, the manufacturer and the investigator(s)/institution(s) where the ATIMP is used) will ensure that the information relating to the traceability and accountability, from the production of ATIMPs to the recipient (participant) receiving the ATIMPs, are archived for a minimum of 30 years after the expiry date of the ATIMP. These requirements will be set out in contractual agreements between the parties and the sponsor.

### **CNGA3/CNGA3 Gene Therapy trial for Achromatopsia**

The following essential documents/traceability data will be retained by the investigator and institution responsible for the human application of the ATIMP:

- Shipping Records for the ATIMP
- Certificate of Analysis of the ATIMP
- Participant identification code list
- ATIMP accountability at the site including final disposition of both used and unused product

These records contain relevant information for traceability purposes and at least the following minimum data set from these records should be kept for 30 years after the expiry date of the product, or longer if required by the terms of the clinical trial authorisation or by the agreement with the sponsor:

- Identification of the investigator/institution
- Identification of the sponsor
- Identification of the manufacturing site
- Product name/code
- Pharmaceutical form, route of administration, quantity of dosage units and strength
- Batch number
- Trial reference code
- Trial participant code
- Participant identification code list (links name of recipient to the trial participant code)
- Product expiry/retest date
- Date of administration
- Participant medical record should also contain the product name/code, the trial reference code, trial participant code and administration dates and doses
- Records of any product that was unused or destroyed at site and its final status

### **6.11 Access to Data**

The investigators/ institutions will permit trial-related monitoring, audits, REC review, and regulatory inspections, providing direct access to source data/documents. Trial participants are informed of this during the informed consent discussion. Participants will consent to provide access to their medical notes.

Requests for access to trial data will be considered, and approved in writing where appropriate, after formal application to MeiraGTx UK II Ltd.

### **6.12 Ancillary and Post-trial Care**

Participants will be invited to participate in a follow-up study after completion of this trial.

### **6.13 Publication Policy**

#### **6.13.1 Trial Results**

All proposed scientific publications will be discussed with and approved by the MeiraGTx UK II Ltd. prior to publication. Since this is an exploratory, open-label, Phase I/II trial, progress and significant findings may be presented at scientific forums/meetings and/or published during the course of the trial. Where the presenter is not a MeiraGTx UK II Ltd. Representative, permission must be sought from MeiraGTx UK II Ltd.

The results of the trial will be disseminated regardless of the direction of effect.

## **7 Ancillary Studies**

There are no currently planned ancillary studies. Any future ancillary studies will be subject to separate funding and will be submitted for ethical and regulatory review as appropriate.

## **8 Appendix: Guidance on Study Conduct during the COVID-19 Pandemic**

This Appendix is intended for all ongoing studies at sites worldwide impacted by COVID-19. The measures outlined in this Appendix are temporary, while access to sites is restricted. As restrictions are lifted, the decision to revert back to the protocol in effect prior to the pandemic should be discussed and agreed with the sponsor.

It is recognised that the Coronavirus Disease 2019 (COVID-19) pandemic may have an impact on the conduct of this clinical study due to, for example, self-isolation/quarantine by participants and study-site personnel; travel restrictions/limited access to public places, including hospitals; study site personnel being reassigned to critical tasks.

In alignment with recent health authority guidance, the sponsor is providing options for study related participant management in the event of disruption to the conduct of the study. This guidance does not supersede any local or government requirements or the clinical judgement of the investigator to protect the health and well-being of participants and site staff. If at any time a participant's safety is considered to be at risk, study intervention will be discontinued, and study follow-up will be conducted.

Scheduled visits that cannot be conducted in person at the study site will be performed remotely/virtually or delayed until such time that on-site visits can be resumed. At each contact, participants will be interviewed to collect safety data. Key efficacy endpoint assessments should be performed if required and as feasible. Participants will also be questioned regarding general health status to fulfil any physical examination requirement.

If visits should be delayed past the visit window as per the schedule of events every effort should be made to see this patient as soon as it is deemed safe to do so whether this is due to the countries' Governing bodies restrictions being uplifted or under the advice of the CI of that site and patient's should not be made to wait until the next protocol visit.

Every effort should be made to adhere to protocol-specified assessments for participants on study intervention, including follow up. Modifications to protocol-required assessments may be permitted after consultation between the participant and investigator, and with the agreement of the sponsor. Missed assessments/visits will be captured in the eCRF for protocol deviations and should be titled 'COVID-19 related'. Discontinuations of study interventions and withdrawal from the study should be documented with the prefix "COVID-19-related" in the case report form (CRF).

The sponsor will continue to monitor the conduct and progress of the clinical study and any changes (eg, delay or discontinuation in recruitment, site monitoring and audits) will be communicated to the sites and health authorities according to local guidance. If a participant has tested positive for COVID-19, the investigator should contact the sponsor's responsible medical officer to discuss plans for study intervention and follow-up. Modifications made to the study conduct as a result of the COVID-19 pandemic should be summarised in the clinical study report.

**GUIDANCE SPECIFIC TO THIS PROTOCOL**

Each patient will be risk assessed on a case by case basis by the PI and his/her research team to decide the appropriate care for the patient.

Item no	Item	Management of Item
1	Missed assessments	Missed assessments will be captured in the EDC system as a deviation with the prefix COVID 19 RELATED.
2	Protocol Deviations	Any deviations to the study protocol due to COVID 19 pandemic will be captured in the EDC system will be entered with the prefix COVID 19 RELATED.
3	Baseline Assessments	Baseline assessments for those patients who have had surgery postponed due to COVID 19 - these baseline assessments will be valid up to 9 months except for Haematology, Biochemistry and Glucose which will need repeating.
4	Patients may be unable to attend study visit during visit window.	
It is acknowledged that this is a global crisis and patients may be put at more risk attending hospital appointments due to route of travel into research facility. If appropriate the sponsor will offer expenses for taxi fares to avoid busy train or bus routes.
 
If scheduled visits cannot be conducted within the visit window the site can schedule an additional visit at the earliest opportunity the patients is able to travel, ensuring no visits are completely missed unless authorised by the sponsor.
 
If patients are unable to reach their research facility but are able to seek help at a local ophthalmologist for urgent concerns this is acceptable, and the sponsor will encourage patients to show any non-trial staff conducting assessments the contact details for the trial staff so that conversations can be had between the trial and non-trial medical staff

6	Patients visits conducted outside of visit window	
Patients will be assessed individually by the sites on a case by case basis and phone interviews may be conducted by sites for all follow up visits up until at least 3 months post-surgery until on-site visits are possible.
 
Patients undergoing telephone assessment will be asked to provide information on any adverse events or other safety concerns.

7	Patients self-quarantined or government implemented quarantine.	If patients and/or their caregiver are under quarantine and unable to leave home, their cases will be assessed by medical monitors and PI as to risk of delayed appointment. (e.g

**CNGA3CNGA3 Gene Therapy trial for Achromatopsia**

		ongoing AEs, date of last appointment, less than 3 months since intervention).
8	
Potential lack of reporting of symptoms due to delayed visits
 
Delayed reporting of SAEs, SARs & SUSARs- Potential for events to not be reported within 24 hours of occurrence
 
Delayed Participant reporting of Adverse Events
	
All participants are provided with emergency cards on enrolment to the study to enable 24-hour contact with study investigators.
 
All events should be reported by an Investigator (as assigned on the delegation log) or another member of the site team, in the Investigators absence and where delegated, within 24 hours of the investigator/site being made aware. Sites have been advised how to still maintain timelines for reporting if impeded by pandemic restrictions.

9	
Emergencies during the study and the provision of emergency contact arrangements:
	
If the participants facing difficulties in contacting the Trial Team in the event of emergencies, they have been provided with an alert card to inform other healthcare providers of their participation in the gene therapy trial. The Trial card includes the 24/7-hour contact number, patients trial code, trial number, brief details of the trial intervention and EudraCT number.

10	
Patients may require NIMPs that they would have collected a scheduled study visit.
	
Site research staff will be in regular contact with their study patients and should they require NIMPs, the site pharmacy will be able to courier them to the patient and charge the cost to the sponsor.

11	
Assessment results outside of window not true representation of protocol stated timepoints
	
Patient safety will be most important factor to consider. Patients will be invited as close to visit window as possible and deviations recorded where applicable.

12	
Questionnaire responses could be incorrect due to expected visit vs actual visit attended.
	
Patient may confuse true answers if questionnaire asks for certain timepoints. Site research staff will explain questionnaire details before patient answers.

13	
Clinician/s and site research staff unavailable due to contraction of virus
	
Site to ensure appropriate staff are available and documented on the delegation log to provide medical cover if the PI is unavailable.

14	
Monitor may not be allowed on site or may be quarantined and unable to visit.
	
Monitors will be encouraged to attend site where possible, if unable will conduct remote monitoring as much as possible and arrange as many visits as is required to get back on track once site re-opens.

**9 Protocol Amendments**

Protocol Version and Date	Reason for Amendment
Protocol v1.0 16Nov2018	Initial version
Protocol v2.0 29Jan2019	Reduction of assessments based on analysis of CNGB3 MGT006 data to reduce assessment burden on participants and clinical sites and addition of optional MRI assessment.
Protocol v3.0	Update to contraception wording on request of MHRA
Protocol v4.0	Change of baseline/screening window prior to surgery from 6 months to 9 months. Addition of Photoaversion Device Questionnaires. Removal of MRI assessment
Protocol v5.0	Updated steroid & surgical risks, and local steroid use detailed.  Guidance included on the management of patients during COVID-19 pandemic  Further details added to exclusion criteria.  Re-illustration of dose escalation table (no changes made)
Protocol v6.0	Removed dose expansion cohort (as this will now take part as a separate Phase II interventional study)  Included details on additional adult cohort taking place in the US.  Corrected inconsistencies

## CNGA3/CNGB3 Gene Therapy trial for Achromatopsia

---

#### **ABBREVIATIONS**

AAV Adeno-Associated Virus ADL activities of daily living

AE adverse event

ATC Anatomical Therapeutic Chemical

ATIMP advanced therapy investigational medicinal product

BMI body mass index CI confidence interval

CNGA3 Cyclic Nucleotide-Gated Cation Channel Beta-3

DLE dose-limiting event ERG electroretinography

ETDRS Early Treatment Diabetic Retinopathy Study

eCRF electronic case report form FST Full-field Stimulus Testing

IDMC Independent Data Monitoring Committee

IVI impact of visual impairment
IVI-A impact of visual impairment adult
IVI-C impact of visual impairment child

MedDRA Medical Dictionary for Regulatory Activities

PA photoaversion

PCR polymerase chain reaction

QoL Quality of Life
SAE serious adverse event
SAP Statistical Analysis Plan
SD standard deviation

SD-OCT spectral domain optical coherence tomography SUSAR suspected unexpected serious adverse reaction

VA Visual Acuity

VRQoL Vision-Related Quality of Life

WHO-DD World Health Organization Drug Dictionary

#### 1. INTRODUCTION

This Statistical Analysis Plan (SAP) specifies definitions of analysis sets, key derived variables, and statistical methods for the analysis of safety and efficacy data for the Phase I/II CNGA3 study (MGT012). This SAP is based on the protocol of study MGT012, v 6.0 16April2021. Titles, mock-ups and programming instructions for all statistical outputs (tables, figures, and listings) are provided in a separate document.

## 1.1. Trial Objectives

The primary research objective is to assess the safety of an AAV8 vector for hCNGA3 gene replacement in the retina based on the primary safety outcome listed in Section 2.1.

The secondary research objective is to determine whether an AAV8 vector for hCNGA3 gene replacement in the retina can improve retinal function, visual function and quality of life.

# 1.2. Trial Design

This is an open-label, non-randomized phase I/II dose-escalation trial to determine the safety and efficacy of subretinal administration of the study agent (ATIMP) in participants with CNGA3-related Achromatopsia. In this dose escalation study, up to 18 participants were administered one of 3 doses of the ATIMP in cohorts of 3 pediatric participants at a time in the first instance. Based on emerging safety data, the Safety and Data Monitoring Committee (SDMC) will make a recommendation on the dose to administer to the next cohort of 3 participants.

Pediatric cases for the purpose of the protocol are defined as participants <16 years in the UK or <18 years in the US.

Safety and efficacy will be assessed for 6 months following the intervention by clinical examination and special investigations according to the schedule in Section 5.6 of the protocol. In line with current CHMP and FDA guidance, the ATIMP safety is further assessed by a separate longer term follow up study of 60 months duration, if the participants / caregiver's consent and only once they have reached the 6-month timepoint in the current study.

Due to the rare nature of the disease, there were no formal sample size calculations performed and no formal hypothesis testing is planned.

#### 2. OUTCOME DEFINITIONS

### 2.1. Primary Safety Outcome

The primary safety outcome is defined as the absence/presence of any of the below events occurring during the 6 weeks following administration, at least possibly related to the ATIMP, not surgery alone:

- Reduction in visual acuity by 15 Early Treatment Diabetic Retinopathy Study (ETDRS) letters or more
- Severe unresponsive inflammation (defined in Section 4.2 of the protocol)

- Infective endophthalmitis
- Ocular malignancy
- Grade III or above non-ocular suspected unexpected serious adverse reaction (SUSAR) (Protocol MGT006, Section 5.11.3.4.2 Severity or Grading of Adverse Events).

This is the same criteria as the dose limiting event in the dose escalation phase.

Overall safety will be assessed for 6 months after the intervention in this study, and a further 4.5 years in a separate long-term follow-up study (Protocol MGT007).

The adverse events preferred terms are identified in Attachment 2.

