#### 4.3.2.1 Dose escalation criteria and Dose Limiting Events

Dose escalation will be managed according to review of available and emerging data on the subjects administered ATIMP top date and the occurrence, if any, of DLE's or medically important events. An SDMC will review data from a minimum of 6 weeks of follow up from each cohort of participants (at least one older child, 11-15 years of age per cohort), before recommending the next dose to be assessed in a further cohort of participants or to additional participants at the same dose level.

A DLE is defined as any of the below occurring during the 6 weeks following administration, at least possibly related to the ATIMP, not surgery alone:

- A reduction in visual acuity by 15 ETDRS letters or more that fails to resolve to within 15 letters of baseline in a 4-week period once prophylactic treatment commences
- Severe unresponsive inflammation (defined below)\*
- Infective endophthalmitis
- Ocular malignancy
- Grade III or above non-ocular SUSAR (see section 5.11.3)

\* Severe unresponsive inflammation will be defined according to the Standardisation of Uveitis Nomenclature (SUN) Working Group grading system (Jabs *et Al.* 2005) i.e.

- anterior chamber cells 3+ (26-50 cells in a field size of 1mm x 1-mm slit-beam), or
- anterior chamber flare 3+ (marked, iris and lens details hazy), or
- vitreous haze 3+ (Ophthalmology 1985; 92:467-71)

that fails to improve by 2 steps (or to grade 0) during a 6-week period.

Review of safety data will be undertaken by the SDMC prior to each dose escalation.

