## 5.5 Outcomes

### 5.5.1 Primary Outcomes

The primary outcome is defined as any of the below occurring during the 6 weeks following administration, at least possibly related to the ATIMP, not surgery alone:

- Reduction in visual acuity by 15 ETDRS letters or more that fails to resolve to within 15 letters of baseline in a 4-week period once prophylactic treatment commences
- Severe unresponsive inflammation
- Infective endophthalmitis
- Ocular malignancy
- Grade III or above non-ocular SUSAR (see section 5.11.3)

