#### **5.10.3.2 Statistical Methods – Primary Outcome Analysis**

The primary outcome is safety of subretinal administration of the ATIMP defined as any of the below occurring during the 6 weeks following administration, at least possibly related to the ATIMP, not surgery alone:

- Reduction in visual acuity by 15 ETDRS letters or more that fails to resolve to within 15 letters of baseline in a 4-week period once prophylactic treatment commences
- Severe unresponsive inflammation
- Infective endophthalmitis
- Ocular malignancy
- Grade III or above non-ocular SUSAR (see section 5.11.3)

The number of DLEs at each dose level will be summarised by cohort and overall.

It is anticipated that the ATIMP will be administered at the MTD in up to 18 participants. Safety data relating to these participants will allow estimation of an upper bound for the true event rate through a 95% confidence interval.

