**CNGA3CNGA3 Gene Therapy trial for Achromatopsia**

Table 6: Assessment of expectedness

Category	Definition
Expected	An adverse event that is classed in nature as serious and which is consistent with the information about the surgery listed in the Investigator Brochure or clearly defined in the protocol. In view of the very limited clinical experience with the ATIMP there are at present no events considered as expected for the ATIMP listed in the current Investigator Brochure.
Unexpected	An adverse event that is classed in nature as serious and which is not consistent with the information about the ATIMP and surgery listed in the Investigator Brochure* or clearly defined in the protocol.

\*This includes listed events that are more frequently reported or more severe than previously reported

The reference document to be used to assess expectedness against ATIMP and surgery is the Investigator Brochure. Procedure-related adverse events cannot be considered expected to the ATIMP. Previous experience with AAV-mediated gene therapy in the retina indicates that the risks are largely limited to the eye. A temporary and/or mild decrease in visual acuity, due to detachment of the retina or post-surgical inflammation, is to be expected after intraocular surgery and is not expected to cause undue discomfort. Therefore, we have defined the success criteria for the primary outcome (safety) as the absence of an adverse event that has a substantial and sustained negative impact on vision, as well as the absence of any non-ocular SUSAR.

Expected events associated with surgery:

- Temporary and/or mild decrease in visual acuity (to hand movements or better for a period of up to 8 weeks), due to detachment of the retina or post-surgical inflammation
- Ocular discomfort
- Epiphora
- Periocular swelling
- Diplopia
- Ptosis
- Subconjunctival or intraocular haemorrhage
- Corneal abrasion
- Retinal tear or detachment
- Wound leak
- Ocular hypotony or raised intraocular pressure
- Overfill or underfill of any intraocular gas tamponade
- Mild intra- or extra-ocular inflammation
- Scleral or conjunctival suture granuloma
- Lens opacity or dislocation
- Systemic adverse events related to sedation or general anaesthesia, including nerve or vascular injury

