#### 5. SAFETY ANALYSES

# 5.1. Primary Safety Outcome

The proportion of participants who experience the primary safety outcome and the corresponding 95% confidence interval (CI) using for the binomial proportion based on the normal approximation with continuity correction will be provided (by age group, dose level and overall). The primary safety outcome will also be listed.

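### SAP 2.1 drops the protocol's non-resolution condition from the visual acuity component of the primary safety outcome, yet says its criteria match the DLE

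*SAP*

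**What the plan says.** SAP 2.1 counts events within 6 weeks of administration that are at least possibly related to the ATIMP and not to surgery alone. Its acuity item reads, in full, "Reduction in visual acuity by 15 Early Treatment Diabetic Retinopathy Study (ETDRS) letters or more". After the list it adds: "This is the same criteria as the dose limiting event in the dose escalation phase". SAP section 1 states: "This SAP is based on the protocol of study MGT012, v 6.0 16April2021".

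The protocol's DLE definition (4.3.2.1) is longer: "A reduction in visual acuity by 15 ETDRS letters or more that fails to resolve to within 15 letters of baseline", within a 4-week period that runs from the start of prophylactic treatment. Protocol 5.5.1 puts the same condition on the primary outcome: a loss "that fails to resolve to within 15 letters of baseline in a 4-week period once prophylactic treatment commences". The condition also appears in the structured trial summary (1.3), the primary objective (4.2.1) and the primary outcome analysis (5.10.3.2).

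SAP 5.1 reports the proportion with the primary safety outcome and a 95% confidence interval by age group, by dose level and overall, and lists the events. Protocol 5.10.3.2 separately requires that "The number of DLEs at each dose level will be summarised by cohort and overall".

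**The concern.** The two definitions classify the same participant differently. A participant who loses 15 or more letters within 6 weeks, has the loss rated at least possibly ATIMP-related, and then recovers to within 15 letters of baseline in the 4-week period is an event under the SAP bullet and a non-event under the protocol. SAP 2.1 supports both readings, one through its bullet and the other through its equivalence sentence.

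The condition has a purpose. Protocol 5.11.3.5.4 expects a temporary fall in acuity after intraocular surgery and for that reason defines success as "the absence of an adverse event that has a substantial and sustained negative impact on vision", together with the absence of any non-ocular SUSAR. The SAP bullet keeps the size of the loss and drops its persistence.

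At stake is who counts in the primary proportion. The trial is open label, and SAP 1.2 already describes dosing in the past tense. If the wording stays open, the definition may be chosen with the outcomes in view.

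**Working it through.** **1. The texts side by side**

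| Place | Loss of 15 or more letters | Must fail to resolve within 4 weeks |
|---|---|---|
| Protocol 1.3 | yes | yes |
| Protocol 4.2.1 | yes | yes |
| Protocol 4.3.2.1 (DLE) | yes | yes |
| Protocol 5.5.1 | yes | yes |
| Protocol 5.10.3.2 | yes | yes |
| SAP 2.1 | yes | absent |

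Nothing else in the SAP restores the condition. SAP 5.1 only reports the outcome, and Attachment 2 gives a single preferred term for reduced acuity. The gap is specific to acuity: for severe unresponsive inflammation, SAP 2.1 refers to protocol 4.2, which carries its own persistence condition.

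**2. Direction.** The SAP acuity set contains the protocol acuity set, because one condition has been removed and nothing added. The SAP proportion can therefore equal or exceed the protocol proportion, never fall below it. The two differ only by resolving losses rated at least possibly ATIMP-related. Loss due to surgery alone is excluded in both documents.

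**3. Effect of one such participant, with no other primary event.** The plan states no figure to reproduce. The exact (Clopper-Pearson) upper 95% limit for x events in n is the 0.975 quantile of Beta(x + 1, n − x). For x = 0 this is 1 − 0.025^(1/n); for example, 1 − 0.025^(1/18) = 18.5%. SAP 5.1 instead specifies the normal approximation with continuity correction, whose upper limit is p + 1.96·√(p(1 − p)/n) + 1/(2n). For 1/18 that is 0.0556 + 0.1058 + 0.0278 = 18.9%.

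| Group | Proportion | Exact upper limit | SAP-method upper limit |
|---|---|---|---|
| Overall, n = 18 | 0% → 5.6% | 18.5% → 27.3% | 2.8% → 18.9% |
| Overall, n = 11 (assumed: 3 × 3 children + 2 adults) | 0% → 9.1% | 28.5% → 41.3% | 4.5% → 30.6% |
| Cohort of 3 | 0% → 33.3% | 70.8% → 90.6% | 16.7% → above 100% |
| Adults, n = 2 | 0% → 50% | 84.2% → 98.7% | 25.0% → above 100% |

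The exact limits are the more meaningful at these sizes. The last column shows what the SAP's own method would give before truncation at 100%.

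**4. Can the condition be programmed?** Acuity is scheduled at D1, D3, W1, W2, W4, W6, W12 and W24 (protocol Table 2), so the letters will be available. The start of the 4-week period is not fixed. Protocol 5.4.1.5 has oral prophylaxis starting one week before administration; 5.4.1.5 and 5.4.2.2.2 also describe prophylaxis given at the end of surgery. In days after dosing:

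- Oral start: −7 + 28 = 21. In the protocol schedule W2 covers days 10 to 18 (14 ± 4) and W4 covers days 21 to 35 (28 ± 7), so day 21 is the first day of the W4 window. The SAP calls the dosing day Day 1, so this is study Day 22, inside its Week 4 window of Days 21 to 36.
- End-of-surgery start: 0 + 28 = 28, the W4 target day.

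Both periods end before the W6 target, day 42. A loss first recorded at W6 is still inside the 6-week outcome window but falls after either 4-week period has closed.

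**The case against.** The strongest reply is that the SAP points to the intended reading. It names protocol v6.0 as its basis, says the criteria are those of the DLE and signals no change, so the bullet looks like a truncated copy. Its derivation may also be settled in the programming instructions, which SAP section 1 places in a separate document that was not available. This makes an oversight likely, and it means one cannot say that the programmer is in fact left to choose. It does not cure the contradiction: the SAP governs the definition, and a subsidiary document should not have to overrule it.

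The second reply is that little turns on it. The analysis is descriptive with no hypothesis test, events are listed, escalation follows the protocol DLE, and the omission can only add events. The affected set is narrow, and protocol 5.11.3.5.4 lists temporary acuity loss of up to 8 weeks as expected after surgery, so many such losses may be attributed to surgery alone. All of this stands and limits the consequence. The causality filter is still no substitute for the missing condition: protocol Table 5 allows a rating of possibly related on timing even when other factors may have contributed.

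Third, the maximum may be 20, because protocol 1.3 gives up to 18 paediatric participants and 4.3 adds 2 adults. One event would then be 1/20 = 5.0% instead of 5.6%, which changes little. Finally, the start of the 4-week period is a separate ambiguity in the protocol. That is correct; it is raised here because the condition cannot be programmed without it.

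**Conclusion.** The point holds. SAP 2.1 omits a condition that the protocol attaches to the acuity event in all five places, and its statement that the criteria equal the DLE is false for acuity. It must be corrected before analysis because it leaves the primary outcome with two incompatible definitions, not because a large numerical effect has been shown.

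No expected number of misclassified participants is claimed, since the documents give no rate. The figures describe one resolving, at least possibly ATIMP-related loss in a participant with no other primary event; n = 11 is an assumption. The bias is towards over-counting harm, and dose escalation is unaffected. Nothing is claimed about what the separate output document contains.

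**What to change.** 1. **Settle the definition in SAP 2.1.** Either restore the protocol's acuity condition in full and derive it from the recorded ETDRS letters plus the investigator's ATIMP causality rating; or declare a deliberate change, delete the sentence equating the criteria with the DLE, and report protocol-defined DLEs by dose level as protocol 5.10.3.2 requires.
2. **Reconcile the start of the 4-week period before programming.** The sponsor should state it identically in protocol and SAP, name the scheduled acuity visit that decides resolution, and say how a loss first recorded at W6 is classified.
3. **Minor.** State whether the Attachment 2 terms only identify candidate events that must then meet SAP 2.1; that reading should be made explicit.
4. **Clerical.** The grading reference in SAP 2.1 cites protocol MGT006, section 5.11.3.4.2; in this protocol (MGT012) grading is in 5.11.3.5.2.

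The cost is SAP wording and programming, with perhaps a short protocol clarification for item 2. Neither documented start needs an extra visit. If the sponsor defines another start, the visit schedule must be checked against it.
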